## STUDY SCHEMA

## STUDY CALENDAR

Procedure	Screening 	Radiosurgery Delivery	Surgical Resection	Post-Surgical Resection Visit	Follow-up  (until 18-months from post-surgical resection visit) (18 months)
Study Day/Visit Day	Day – 30 to Enrollment	Day 1	Day 2 (+8 days)	1-month ±7 days from radiosurgery	Every 3 months ±14 days
Informed Consent	X				
AE Reporting	X	X	X	X	
Concomitant Medications	X	X	X	X	X
SRS		X		X	
Physical Exam 	X			X	X
Medical History	X				
ECOG Performance Status	X			X	X
Pregnancy Test (Serum or Urine) 	X				
Neurocognitive Testing 	X				
QOL Questionnaire 	X			X	X
MRI (Brain) 	X			X	X

1. All screening procedures must occur within 30 days prior to enrollment. Treatment must start within 14 days of enrollment.
2. If a subject has disease progression/relapse or subject withdrawal, then they will be followed as per follow-up requirements.
3. Including height and weight on screening. Temperature, HR, RR, BP and O2 sats or as per institutional standards at all timepoints.
4. For women of childbearing potential, a negative pregnancy test (serum or urine) must be obtained within 30 days prior to the first study intervention.
5. Neurocognitive testing: Multilingual Aphasia Examination Controlled Oral Word Associated Test (COWAT), Trail Making Test, Parts A and B (TMT), and Hopkins Verbal Learning Test-Revised (HVLT-R).
6. QOL Questionnaire: MDASI-BT, EQ-5D-5L.
7. MRI (brain) w/ contrast. Radiographic assessments will be completed as per RANO criteria (see Appendix 3).

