## 1.5 Toxicity

Multiple studies report worsened cognitive decline and quality of life with the addition of WBRT to either SRS or surgery for a limited number of brain metastases. Given evidence for WBRT-related toxicity along with the lack of clear survival benefit with the addition of WBRT (and potentially a survival benefit with SRS alone in certain populations), the current trend for management of limited brain metastases now favors surgery (+/- postoperative SRS) or SRS alone with reservation of WBRT as a salvage option. A number of studies are now evaluating the use of SRS in patients with multiple (more than four) brain metastases. According to a recently published systematic review, SRS may be considered an option for patients with greater than four brain metastases provided the total tumor volume does not exceed 13 cc and no single metastasis is larger than 3 cc in volume. While postoperative WBRT carries the cognitive and quality of life toxicities discussed above, SRS carries the risk of CNS necrosis (up to 23%). In an effort to reduce the risk of radiation necrosis with SRS applied to larger volumes while retaining efficacy, different dose and fractionation schedules are under investigation.

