## **2.3 Primary Endpoint**

1. Feasibility for this study will be defined as 50% of enrolled study subjects undergoing the surgical resection as per the protocol.
2. Measure rate of local control at the resection cavity any new tumors by post-treatment MRI.

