## **2.4 Secondary Endpoint(s)**

1. CNS progression-free survival and overall survival will be evaluated at six, 12, and 18 months following surgical resection.
2. Rates of leptomeningeal carcinomatosis using preoperative GK-SRS will be documented and compared to historically cited rates for postoperative GK-SRS.
3. Incidence of radiation necrosis will be measured by post-treatment MRI.
4. Quality of life measures will be collected and will be compared to historically cited data.

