## APPENDIX 3. RESPONSE CRITERIA FOR CNS METASTASES PROPOSED BY RANO-BM

	Complete Response	Partial response	Stable disease	Progressive disease
Target lesions	None	≥30% decrease in sum longest distance relative to baseline	<30% decrease relative to baseline but <20% increase in sum longest distance relative to nadir	≥20% increase in sum longest distance relative to nadir*
Non-target lesions	None	Stable or improved	Stable or improved	Unequivocal progressive disease*
New lesion(s)†	None	None	None	Present
Corticosteroids	None	Stable or decreased	Stable or decreased	Not applicable‡
Clinical status	Stable or improved	Stable or improved	Stable or improved	Worse*
Requirement for response	All	All	All	Any‡

\*Progression occurs when this criterion is met.

†A new lesion is one that does not present on prior scans and is visible in a minimum of two projections. If a new lesion is equivocal, for example because of its small size, continued therapy can be considered, and follow-up assessment will clarify if the new lesion is new disease. If repeat scans confirm there is definitely a new lesion, progression should be declared using the date of the initial scan showing the new lesion. For immunotherapy-based approaches, new lesions alone do not define progression.

‡Increase in corticosteroids alone will not be taken into account in determining progression in the absence of persistent clinical deterioration.

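### Appendix 3 has no rule for radiation-effect enlargement, so one MRI can feed progression, necrosis or both, and nothing separates necrosis from recurrence at the cavity

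*Combined protocol and SAP*

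**What the plan says.** Section 2.3 gives the second primary endpoint as "Measure rate of local control at the resection cavity any new tumors by post-treatment MRI". Section 2.4 gives a secondary endpoint as "Incidence of radiation necrosis will be measured by post-treatment MRI". The Study Calendar schedules one series of contrast brain MRIs (screening, the post-surgical visit, then every three months), and its footnote 7 says: "Radiographic assessments will be completed as per RANO criteria (see Appendix 3").

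For target lesions, Appendix 3 sets progression at "≥20% increase in sum longest distance relative to nadir", with the note "Progression occurs when this criterion is met". Clear progression of non-target lesions, a new lesion or clinical worsening is also enough. The footnotes make three allowances: an equivocal new lesion may await a repeat scan, with progression dated back to the first scan; new lesions alone do not define progression under immunotherapy; and a steroid increase alone does not count without lasting clinical decline. None concerns enlargement of a lesion or cavity that has been irradiated.

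Section 3.2 has SRS given to all metastases, with only the resectable ones removed. Section 5.1.2 has residual disease after subtotal resection left under observation. Irradiated tissue therefore remains in the brain during follow-up.

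**The concern.** Radiation necrosis can enlarge and enhance on contrast MRI, as recurrent tumor does. The plan gives no diagnostic criteria for necrosis, no definition of cavity failure, no confirmatory scan for growth at a treated site, and no adjudication. The pathology it describes comes from the planned resection, one to 10 days after SRS, and so cannot classify growth that appears later.

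Two results are exposed. At an unresected treated lesion or residual tumor, Appendix 3 followed as written can turn radiation effect into a CNS progression event. At the cavity, a reader has no written basis for choosing between recurrence and necrosis, and may record one, both or neither. This matters because section 2 hypothesizes better local control than with postoperative radiosurgery, section 1.7 presents less necrosis as an advantage of the preoperative approach, and section 3.2 compares both rates with historical ones.

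**Working it through.** **Inputs.** 10 completed patients (Protocol Summary, 3.1); assumed local control 85%, hence 15% failure (7.1); exact binomial interval (7.2); necrosis with SRS of up to 23% (1.5); no necrosis in the neoadjuvant series described in 1.7. The documents give no share of events misread, so f (necrosis read as failure) and g (recurrence read as necrosis) are assumptions from 0 to 1. A 5% necrosis rate is an assumed low value.

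**Step 1: the rule applied by site.**
- *Unresected treated lesion:* growth enters the target-lesion sum or the non-target assessment. If the threshold is met, progression is declared whatever the cause. This reaches CNS progression-free survival, not control at the resection cavity.
- *Residual tumor after subtotal resection:* the same rule applies.
- *Cavity after gross total resection:* there may be no target lesion to measure, and the plan does not say how Appendix 3 becomes a cavity result. Recurrence and necrosis are simply not distinguished.
- *Clinical worsening caused by necrosis:* this meets a progression criterion in its own right.

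The size criterion is a patient-level sum. If k target lesions have equal longest distances at nadir and only one grows, it must grow by 20% × k to trigger progression: 20% for one lesion, 40% for two, 60% for three. Three is the most that can remain unresected when up to four are allowed and at least one is removed.

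**Step 2: the plan's own figure.** The plan has no figure for misclassification. Its only precision figure is an interval width of at most 0.40 (7.1). By the exact method the width is 0.531 at 8/10, 0.442 at 9/10 and 0.308 at 10/10, so at these counts 0.40 is met only at 10/10. That is a separate matter and nothing below depends on it.

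**Step 3: one reclassified cavity event.** 1/10 = 10 points.
- 9/10: exact 95% CI 0.555–0.997
- 8/10: exact 95% CI 0.444–0.975

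**Step 4: outer bounds, with all necrosis placed at the cavity.** Let r be the necrosis rate. Apparent local control is 0.85 − f·r if necrosis and recurrence never coincide, or 0.85 × (1 − f·r) if they are independent.

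| r | f | never coincide | independent |
|---|---|---|---|
| 0 | any | 0.85 | 0.85 |
| 0.05 | 1 | 0.80 | 0.81 |
| 0.23 | 0.5 | 0.735 | 0.752 |
| 0.23 | 1 | 0.62 | 0.65 |

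In the other direction, apparent local control is 0.85 + 0.15·g. It reaches 1.00 at g = 1, with the necrosis rate raised by 15 points.

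**Step 5: would a necrosis case be expected at all?** The chance of at least one in 10 patients is 1 − 0.77^10 = 0.93 at 23%, and 1 − 0.95^10 = 0.40 at the assumed 5%.

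**The case against.** The strongest reply is that Appendix 3 is not a pure size rule, that its threshold applies to a sum which one enlarging site may not move enough, and that nothing says cavity control is scored by that threshold. All of this stands. A reader might infer that the 20% rule directly turns cavity necrosis into local failure; the documents do not support that, because the link from Appendix 3 to the cavity is never stated. What they show at the cavity is a missing definition.

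A reader might also count growth of unresected lesions against local control. Section 2.3 places local control at the resection cavity, so that growth bears on CNS progression-free survival only.

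The stakes are limited too. Sections 7.1 and 7.3 put feasibility ahead of efficacy, and the two intervals in Step 3 overlap heavily. That lowers the urgency. It does not remove the gap, because local control is a named primary endpoint with its own estimate and interval in 7.2. Nor do the other criteria in Appendix 3 help, since none of them tells necrosis from tumor.

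**Conclusion.** The point holds, with medium confidence, as something that should be fixed. Followed as written, Appendix 3 can score radiation-effect enlargement as CNS progression, and at the cavity no rule separates recurrence from necrosis. The firm measure of size is 10 points of local control per reclassified cavity event among 10 patients.

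It would be tempting to say that local control could read anywhere from 62% to 100%. Those are extreme bounds. The low end (62–65%) needs a general SRS rate quoted as a maximum, all of it at the cavity and all misread. The high end needs every recurrence misread. The documents give no misread share, section 1.7 expects resection to remove tissue at risk, and the neoadjuvant series cited there saw no necrosis. Nor can it be said that the rates are uninterpretable against history, because the documents do not show how the historical series classified such events.

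**What to change.** Add a paragraph to Appendix 3 and a sentence to 2.4, stated to govern endpoint scoring only, with no effect on clinical management or on decisions about salvage therapy:

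- Extend the existing rule for equivocal new lesions to enlargement at any SRS-treated site: cavity, residual tumor or unresected lesion. Score the first such scan as indeterminate.
- Classify it as recurrence or radiation effect from subsequent scheduled MRI, or from histology if tissue is obtained for clinical reasons, using criteria written before outcomes are read. The steroid record should not be relied on to decide, since nothing in the documents shows that it separates the two.
- Date confirmed recurrence to the first enlarging scan.
- Do not count growth judged to be radiation effect as local failure or CNS progression. Allow a patient to have both events where both are established.
- Say how Appendix 3 is applied to a cavity with no measurable target.
- Report the number left indeterminate, and give local control and CNS progression-free survival with those cases counted as all recurrence and as all necrosis.

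This needs no added scan, reader or procedure. The costs are a delay of about three months in classifying some events, late events that may stay indeterminate, and a reported range that may be wider.

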# **3 STUDY DESIGN**

## **3.1 General Description**

This is a single-arm, single-center, pilot study in which 10 completed patients with one to four brain metastases diagnosed on brain MRI within the past 30 days will be evaluated for study eligibility and enrolled as appropriate.

## **3.2 Design of the Current Study**

Enrolled patients will receive GK-SRS to all metastases followed by surgical resection of resectable metastases within one to 10 days following GK-SRS. Pathologic specimens will be analyzed, and the patient will enter a standard pattern of surveillance (brain MRI every three months for two years).

Quality of life will be assessed every three months, and neurocognitive evaluations will be performed every six months. These parameters will be compared to baseline testing performed at the time of enrollment. Local control, CNS progression-free survival, overall survival, rates of leptomeningeal carcinomatosis, rates of radiation necrosis, and steroid requirements will also be documented and compared with historically reported rates.

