Study Intervention Description	Enrolled patients will receive SRS to all metastases followed by surgical resection of resectable metastases within one to 10 days following

	SRS. Pathologic specimens will be analyzed, and the patient will enter a standard pattern of surveillance (brain MRI every three months for two years).
Number of Subjects	Up to fifteen subjects will be enrolled in this study to attain ten completed subjects.
Estimated Time to Complete Enrollment:	Approximately two years.

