#### Inclusion Criteria

1. Voluntary written consent must be given before performance of any study-related procedure that is not part of standard medical care, with the understanding that consent may be withdrawn by the subject at any time without prejudice to future medical care.
2. English speaking.
3. Female or male subject's  $\geq$  18 years old at the time of informed consent.
4. Radiographically confirmed solid tumor brain metastases.
5. Criteria for surgical resection of at least one metastasis per neurosurgeon discretion.
6. Stereotactic radiosurgery candidate per radiation oncologist discretion.
7. A diagnostic MRI brain or CT head demonstrating the presence of one to four solid tumor brain metastases and lesion to be resected no more than 5 cm in any direction, performed within 30 days prior to stereotactic radiosurgery.
8. For known and unknown primary, ds-GPA estimated median survival no less than six months.
9. Surgical resection able to be performed within one to 10 days after radiosurgery.
10. Patients currently on cytotoxic chemotherapy or immunotherapy are eligible, not including anti-VEGF therapy.
11. Female subjects who:
  - a. Are postmenopausal for at least one year before the screening visit, OR
  - b. Are surgically sterile, OR

If they are of childbearing potential:

- i. Agree to practice one highly effective method and one additional effective (barrier) method of contraception, at the same time, from the time of signing the informed consent through four months after the last study Intervention (female and male condoms should not be used together), OR
- ii. Agree to practice true abstinence, when this is in line with the preferred and usual lifestyle of the subject. (Periodic abstinence [e.g., calendar, ovulation, symptothermal, post-ovulation methods] withdrawal, spermicides only, and lactational amenorrhea are not acceptable methods of contraception.)

CRC Initials: \_\_\_\_\_

Date: \_\_\_\_\_

Investigator/Enrolling Physician Initials: \_\_\_\_\_

Date: \_\_\_\_\_

12. Male subjects, even if surgically sterilized (i.e., status post-vasectomy), who:

- Agree to practice effective barrier contraception during the entire study treatment period from the time of signing the informed consent through and through four months after the last study intervention (female and male condoms should not be used together), OR

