### **Exclusion Criteria**

- Patients who received anti-VEGF therapy within six weeks prior to enrollment, as there is increased risk of fatal brain hemorrhage with surgical resection.
- Non-English speaking.
- Major medical illnesses or psychiatric impairments, which in the investigator's opinion will prevent administration or completion of the protocol therapy and/or interfere with surveillance.
- Patients with more than four brain metastases on MRI brain.
- Lesion to be resected is more than 5 cm in any dimension.
- Patients with leptomeningeal metastases documented by MRI or CSF evaluation.
- Previous whole-brain radiation therapy.
- Previous radiation therapy to the lesion to be resected.
- Planned adjuvant focal therapy including additional radiation therapy to the brain.
- Not a surgical candidate per neurosurgeon discretion.
- Not a stereotactic radiosurgery candidate per radiation oncologist discretion.
- Surgery unable to be performed between one to 10 days after radiosurgery.
- Women who are pregnant or nursing as treatment involves unforeseeable risks to the fetus or child.
- Patients who have a known or unknown primary and have an estimated median survival of less than six months per ds-GPA.

*"I have reviewed all inclusion and exclusion criteria and confirm the subject is eligible."*

---

(CRC Signature)

---

(Date)

---

(Investigator/Enrolling Physician Signature)

---

(Date)

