#### **4.9 End of Study Definition**

A participant is considered to have completed the study if he or she has completed all phases of the study including the last visit or the last scheduled procedure shown in the calendar of events or has been discontinued.

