### 10.4 Case Report Forms

The principal investigator and/or his/her designee will prepare and maintain adequate and accurate participant case histories with observations and data pertinent to the study. Study-specific case report forms (CRFs) will document safety and treatment outcomes for safety monitoring and data analysis. All study data will be entered into OnCore® via standardized CRFs, in accordance with the study calendar, using single data entry with a secure access account. The clinical research coordinator will complete the CRFs as soon as possible upon completion of the study visit; the investigator will review and approve the completed CRFs.

The information collected on CRFs shall be identical to that appearing in original source documents. Source documents will be found in the patient's medical records maintained by MCWCC personnel. All source documentation should be kept in separate research folders for each patient.

In accordance with federal regulations, the investigator is responsible for the accuracy and authenticity of all clinical and laboratory data entered onto CRFs. The principal investigator will

approve all completed CRFs to attest that the information contained on the CRFs is true and accurate.

All source documentation and data will be available for review/monitoring by the MCWCC DSMC and regulatory agencies.

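### The study calendar contradicts the protocol text twice: it leaves out the six-monthly neurocognitive tests, and its resection window closes one day early

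*Combined protocol and SAP*

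**What the plan says.** **Neurocognitive testing.** Section 3.2 commits to repeated testing: "neurocognitive evaluations will be performed every six months. These parameters will be compared to baseline testing performed at the time of enrollment". In the Study Calendar, the row "Neurocognitive Testing 5" has one mark, under Screening. Its footnote lists the battery ("Multilingual Aphasia Examination Controlled Oral Word Associated Test (COWAT), Trail Making Test, Parts A and B (TMT", and the HVLT-R) and gives no repeat time. The rows for quality of life, brain MRI, ECOG status and physical exam each carry three marks, the last under Follow-up, where visits run every three months to 18 months.

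**Resection window.** The calendar puts radiosurgery on Day 1 and resection on Day 2 with an allowance of 8 further days. The Protocol Summary has "surgical resection of resectable metastases within one to 10 days following" SRS. Section 3.2, section 5.1 and section 5.1.2 give the same interval, and both eligibility lists repeat it: "Surgical resection able to be performed within one to 10 days after radiosurgery" as an inclusion criterion and "Surgery unable to be performed between one to 10 days after radiosurgery" as an exclusion.

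**Role of the calendar.** Section 10.4 states: "All study data will be entered into OnCore® via standardized CRFs, in accordance with the study calendar". Section 4.9 defines a participant's completion by all phases including "the last visit or the last scheduled procedure shown in the calendar of events", or by discontinuation.

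**The concern.** The document gives staff two different instructions on two points and does not say which prevails.

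On neurocognition, a coordinator who builds visits and case report forms from the calendar collects a baseline battery and nothing after it. The only stated use of the baseline scores is comparison with later ones. A missed six-month test cannot be done afterwards, and section 7.3 plans no imputation. Sections 1.3 and 1.5 cite cognitive decline after whole-brain radiation as a reason for the move towards radiosurgery, so these data bear on the trial's rationale even though they are not an endpoint.

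On the window, primary endpoint 1 (section 2.3) calls the approach feasible if half of enrolled subjects undergo resection in accordance with the protocol. The calendar is part of the protocol, so a resection exactly 10 days after radiosurgery can be classified either way in a trial of at most 15 patients.

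**Working it through.** **1. Neurocognitive sessions**

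Inputs from the documents: six-monthly testing (section 3.2); follow-up to 18 months (Study Calendar); 10 completers from up to 15 enrolled (Protocol Summary); ds-GPA estimated median survival of at least six months (section 4.5, inclusion criterion 8).

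- Post-baseline sessions under section 3.2 to 18 months: months 6, 12 and 18, so 3 per patient.
- Post-baseline sessions marked in the calendar: 0.
- For 10 completers: 10 × 3 = 30 sessions not scheduled.

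To allow for deaths among 15 enrolled, assume exponential survival with median *m* months and no other dropout. The proportion alive at month *t* is 2^(−*t*/*m*), and expected sessions are 15 × [S(6) + S(12) + S(18)].

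| Assumed median (months) | S(6) + S(12) + S(18) | Expected sessions, 15 enrolled |
|---|---|---|
| 6 | 0.500 + 0.250 + 0.125 = 0.875 | 13.1 |
| 12 | 0.707 + 0.500 + 0.354 = 1.561 | 23.4 |
| 24 | 0.841 + 0.707 + 0.595 = 2.143 | 32.1 |

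Only the six-month figure has a link to the documents, as the eligibility floor. The other two medians show the range.

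**2. Resection window**

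- Calendar: Day 2 + 8 = Day 10. With radiosurgery on Day 1, that is 10 − 1 = 9 days after it. The window is 1 to 9 days.
- Text: 1 to 10 days after Day 1 is Day 2 to Day 11, that is, Day 2 + 9.
- Difference: one day at the upper end, so one of the 10 permitted days is lost.

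Counting the radiosurgery day as day 1 does not reconcile the two. The upper limit would become Day 10, but the lower limit would become Day 1, and the calendar starts at Day 2.

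**3. Effect on primary endpoint 1**

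Let *p* be the probability that an enrolled patient is resected 1 to 10 days after radiosurgery, and *q* the share of those resections that fall on day 10. Neither is in the documents, so both are assumed. Patients are taken as independent. Feasibility needs at least *k* resections: *k* = 5 of 10, or 8 of 15 (half of 15 is 7.5). The probability that the two readings give opposite verdicts is

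P(Bin(*n*, *p*) ≥ *k*) − P(Bin(*n*, *p*(1 − *q*)) ≥ *k*).

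| *p* | *q* | *n* = 10, *k* = 5 | *n* = 15, *k* = 8 |
|---|---|---|---|
| 0.60 | 0.05 | 5.4% | 7.7% |
| 0.60 | 0.10 | 11.7% | 16.3% |
| 0.70 | 0.05 | 3.1% | 4.1% |
| 0.70 | 0.10 | 7.3% | 9.9% |
| 0.80 | 0.05 | 1.0% | 0.9% |
| 0.80 | 0.10 | 2.8% | 3.0% |
| 0.90 | 0.05 | 0.1% | 0.04% |
| 0.90 | 0.10 | 0.5% | 0.3% |

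For example, with *n* = 15, *p* = 0.70 and *q* = 0.10, the two terms are 0.950 and 0.851, which differ by 0.099.

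**The case against.** Both mismatches are plainly there; the argument is about their weight.

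- **The window is a one-day slip that the text resolves.** Six statements agree against one calendar cell, so anyone deciding whether a resection followed the protocol has an obvious answer. This largely stands: it is why the cell, not the text, should change. It does not remove the second reading, because the protocol sets no order of precedence.
- **The verdict probabilities rest on chosen inputs.** This stands. Eligibility already requires that surgery be possible within the window, so a resection rate above 80% is plausible, and at 90% the probability is at most 0.5%. At 60% it reaches 16%. The figures show the order of size only.
- **Neurocognition is not in section 2 and has no analysis in section 7.** This stands and limits the consequence. Section 3.2 still promises the testing and the comparison.
- **Section 4.9 adds little.** This stands: the 18-month visit, with MRI and quality of life, fixes completion whether or not cognitive tests are marked. Section 10.4 carries more weight, since it ties data entry to the calendar, although it does not say that the calendar overrides section 3.2.
- **Three sessions is a choice of horizon.** Section 3.2 also describes two years of surveillance MRI, over which six-monthly testing would give four sessions. The count of three follows the calendar's 18-month follow-up.

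A fault in reading the table from the PDF could be suspected, but the neighbouring rows keep their Follow-up marks and the footnote is silent on timing too.

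**Conclusion.** The concern holds on both points.

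The neurocognitive omission is the main one. The calendar schedules none of the three post-baseline sessions per patient that section 3.2 implies over 18 months. That is 30 sessions for 10 completers, or roughly 13 to 32 for 15 enrolled under the assumed exponential survival. The loss occurs if staff work from the calendar rather than section 3.2, and missed sessions could not be recovered. No endpoint in section 2 is affected.

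The window error is certain as arithmetic (9 days against 10) and small in effect. Only a resection at exactly 10 days is classified differently. The chance that this reverses the feasibility verdict is about 1 to 4% if 5% of in-window resections fall on day 10, and 3 to 10% if 10% do, at assumed resection rates of 70 to 80%. It is negligible at 90%. No sample size, power or type I error figure depends on either point. Both should be corrected.

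**What to change.** 1. In the Study Calendar, mark neurocognitive testing under Follow-up, and add to footnote 5 that the battery is repeated at the 6-, 12- and 18-month visits. If testing to two years is intended, say so instead and extend follow-up to match.
2. Change the calendar's resection cell to Day 2 (+9 days), so that it ends on Day 11 and a resection 10 days after radiosurgery counts towards primary endpoint 1, as the text intends.

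The cost is two calendar cells and one footnote in a single amendment. Testing at 6, 12 and 18 months fits the existing three-monthly visits, so no visit is added. The burden on patients is the testing time that section 3.2 already commits to.
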